6.3 Missing Data Imputation

No data will be imputed for any efficacy or safety analyses except for analyses of the HCV RNA endpoints.

HCV RNA values will be selected for the SVR₁₂ analysis based on defined visit windows. When there is no HCV RNA value in a visit window based on defined visit windows, the closest values before and after the window, regardless of the value chosen for the subsequent and preceding window, will be used for the flanking imputation described below.

If a subject has a missing HCV RNA value at a post-Day 1 visit, but with undetectable or unquantifiable HCV RNA levels at both the preceding value and succeeding value, the HCV RNA level will be considered undetectable or unquantifiable, respectively, at this visit for this subject. For SVR₁₂ analysis, if there is no value in the appropriate window

after flanking imputation but there is an HCV RNA value after the window, then it will be imputed into the SVR₁₂ window. Similarly, for SVR₂₄ analysis, if there is no value in the appropriate window after flanking imputation but there is HCV RNA value after the window, then it will be imputed into the SVR₂₄ window.

If a subject starts another treatment for HCV, then all HCV RNA and PRO values for this subject measured on or after the start date of the new HCV treatment will be excluded from analyses. The subject will be considered a failure for summaries of viral response at all time points after the start of the new HCV treatment.

HCV RNA < LLOQ Analyses for SVR

If a subject is missing an HCV RNA value for the visit window associated with the analysis of SVR after performing the imputations described above, then this value will be imputed with an HCV RNA value from a local laboratory if present; otherwise, the HCV RNA value for this visit will be missing. Subjects with missing HCV RNA data in the analysis window, after imputations, will be imputed as a failure.

HCV RNA Analyses for Relapse and Virologic Failure

If HCV RNA values from the central laboratory are missing but a local laboratory value is present in the appropriate time period, then the local laboratory value will be used to assess post-treatment relapse and on-treatment virologic failure.

Missing Data Imputation for PRO Questionnaires

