EOTR (end of treatment response) = HCV RNA < LLOQ in the Week 12 window for 12-week regimen, Week 8 window for 8-week regimen, and Week 6 for 6-week regimen.

SVR₄ = HCV RNA < LLOQ in the SVR₄ window (4 weeks after the last actual dose of study drug) without any confirmed quantifiable (\geq LLOQ) post-treatment value before or during that SVR window.

SVR₁₂ = HCV RNA < LLOQ in the SVR₁₂ window (12 weeks after the last actual dose of study drug) without any confirmed quantifiable (\geq LLOQ) post-treatment value before or during that SVR window.

SVR₂₄ = HCV RNA < LLOQ in the SVR₂₄ window (24 weeks after the last actual dose of study drug) without any confirmed quantifiable (\geq LLOQ) post-treatment value before or during that SVR window.

Relapse₁₂ = confirmed HCV RNA \geq LLOQ between end of treatment and 12 weeks after last actual dose of active study drug (up to and including the SVR₁₂ assessment time point) for a subject with HCV RNA < LLOQ at Final Treatment Visit who completes treatment, excluding re-infection as described below.

Relapse₂₄ = confirmed HCV RNA \geq LLOQ during SVR₂₄ window among subjects who achieved SVR₁₂ and have data available during the SVR₂₄ window, excluding re-infection.

Relapse_{late} = confirmed HCV RNA \geq LLOQ at any time after the SVR₂₄ assessment time point for a subject who achieved SVR₂₄ and has post-SVR₂₄ HCV RNA data available, excluding re-infection.

Relapse_{overall} = confirmed HCV RNA \geq LLOQ between end of treatment and up to and including the last HCV RNA measurement collected in the PT Period for a subject with HCV RNA < LLOQ at Final Treatment Visit who completes treatment. Completion of treatment is defined as a study drug duration \geq 37 days, \geq 49 days and \geq 77 days for planned treatment duration of 6 week, 8 weeks and 12 week, respectively. Also, include a

summary of Relapse_{overall} for subjects who prematurely discontinued treatment, excluding re-infection.

For relapse analyses, the completion of treatment is defined as above. If the last available post-treatment value is \geq LLOQ, then the subject will be considered a relapse (i.e., will not require confirmation). Relapse analyses will exclude subjects who do not have any post-treatment HCV RNA values.

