10.6 Additional Efficacy Analyses

The following additional efficacy endpoints will be summarized and analyzed for each treatment arm:

- All reasons for not achieving SVR₁₂ for subjects who do not achieve SVR₁₂;
- Number and percentage with unquantifiable HCV RNA at each post-baseline visit throughout the Treatment Period (using data from the central laboratory as observed, i.e., no imputation for missing data);
- The percentage of subjects with HCV RNA < LLOQ 24 weeks after the last actual dose of study drug (SVR₂₄);
- All reasons for not achieving SVR₂₄ for subjects who do not achieve SVR₂₄.
- Time to suppression of HCV RNA (defined as the study day of the first of two successive HCV RNA < LLOQ) during the Treatment Period.

In the above analyses that use the number and percentage of responders, the rates and 2-sided 95% Wilson score confidence interval for a binomial proportion will be calculated.

For HCV RNA levels, the time to suppression during treatment will be calculated for each subject, and the median time will be estimated using Kaplan-Meier methodology for right censored observations.

Imputations for missing data will be performed as described in Section 6.3 for analyses of SVR, RVR, and EOTR where a missing response will be imputed as a failure after performing the described imputation. All other endpoints will be presented using data as observed.

The number and percent of subjects who fail to suppress HCV RNA and received at least 6 weeks of treatment (active study drug duration \geq 38 days) will be tabulated along with the subject numbers corresponding to the subjects who failed to suppress.

The number of subjects who breakthrough at any time during treatment and within each protocol-specified visit (defined in [Table 2](#), [Table 3](#), and [Table 4](#)) will be summarized along with a corresponding listing displaying the subject numbers at the first occurrence of breakthrough.

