The number of completers (defined as study drug duration \geq 77 days, \geq 49 days, \geq 38 days for 12-week, 8-week, 6-week of treatment, respectively) with final on treatment HCV RNA $<$ LLOQ who relapse within the SVR₄ window, within the SVR₁₂ window, within the SVR₂₄ window (defined in [Table 5](#)), and anytime post-treatment (study drug end day \geq 3) will be summarized along with a corresponding listing displaying the first occurrence of relapse. A similar table and listing will be provided of Preterm Relapses for subjects who do not complete treatment (defined as study drug duration $<$ 77 days, $<$ 49 days, $<$ 38 days for 12-week, 8-week, 6-week of treatment, respectively) with HCV RNA $<$ LLOQ at the Final Treatment visit.

The concordance between SVR₁₂ and SVR₂₄ will be assessed by agreement between SVR₁₂ and SVR₂₄ and by the positive predictive value (PPV) and the negative predictive value (NPV) of SVR₁₂ on SVR₂₄. The agreement between SVR₁₂ and SVR₂₄ is defined as the number of subjects achieving both SVR₁₂ and SVR₂₄ and the number of subjects not achieving both SVR₁₂ and SVR₂₄ out of all subjects in the ITT population. The PPV of SVR₁₂ on SVR₂₄ is the proportion of subjects who achieve SVR₂₄ out of all subjects who achieved SVR₁₂. The NPV of SVR₁₂ on SVR₂₄ is the proportion of subjects who do not achieve SVR₂₄ out of all subjects who do not achieve SVR₁₂.

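### The SVR12–SVR24 agreement, PPV and NPV mix virologic concordance with loss to follow-up and imputation; an observed-data version should be added beside them

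*SAP*

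**What the plan says.** SAP 10.6 defines three concordance measures. Agreement counts subjects who succeed at both time points or fail at both, "out of all subjects in the ITT population". For PPV, "The PPV of SVR₁₂ on SVR₂₄ is the proportion of subjects who achieve SVR₂₄ out of all subjects who achieved SVR₁₂". For NPV, "The NPV of SVR₁₂ on SVR₂₄ is the proportion of subjects who do not achieve SVR₂₄ out of all subjects who do not achieve SVR₁₂". None is limited to subjects with HCV RNA data at both time points.

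The SVR statuses that feed them come from these rules:

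- **Missing as failure.** SAP 6.3: "Subjects with missing HCV RNA data in the analysis window, after imputations, will be imputed as a failure". SAP 10.6 repeats this for SVR, "where a missing response will be imputed as a failure after performing the described imputation".
- **Filling SVR12.** An empty SVR12 window is first filled from the values on either side if both are unquantifiable. If there is still no value "after flanking imputation but there is an HCV RNA value after the window, then it will be imputed into the SVR₁₂ window". An empty SVR24 window can likewise be filled from a later value.
- **Windows.** SAP Table 5 sets SVR12 at Study Drug End Days 57–126 and SVR24 at Days 127–210, with no gap between them.
- **Carry-forward.** SAP 10.1 allows SVR24 only if there is no confirmed quantifiable "post-treatment value before or during that SVR window".

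**The concern.** Missing-as-failure is a conservative choice for a response rate. In a concordance measure it acts on two variables at once, and it has no single conservative direction. A responder who stops attending after the SVR12 window looks the same as one who relapsed. A subject who left before that window looks like a confirmed prediction of failure. A subject who missed the SVR12 window and came back at PT Week 24 can have both statuses set by one sample, so they cannot disagree.

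What is at stake is the reading of a descriptive table. A PPV below 100% would suggest that SVR12 missed late relapses when there may have been none. A PPV or agreement of 100% could in turn hide a late relapse.

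**Working it through.** **The plan's own figures.** SAP 4.3 gives Wilson intervals for an observed SVR12 rate of 90%. Recomputed, 9/10 gives (59.6%, 98.2%) and 18/20 gives (69.9%, 97.2%); both match. The SAP gives no figure for agreement, PPV or NPV.

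**Inputs.** N = 70 and SVR12 = 90% (SAP 4.3), so 63 responders and 7 non-responders. The documents give neither a rate of loss after the SVR12 window nor a rate of late relapse. Both are assumed below: 0, 3 or 6 losses (0 to about 10% of 63) and 0, 1 or 3 late relapses.

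**Step 1: how the rules classify a subject** (scheduled visits at Days 14, 28, 56, 84, 168, 252 and 336; local-laboratory values and new HCV therapy left out)

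| Pattern | SVR12 | SVR24 |
|---|---|---|
| Negative at Day 84, nothing after | yes | no (missing) |
| No value from the SVR12 window onward | no (missing) | no (missing) |
| SVR12 window empty, later values negative | yes (filled) | yes |
| SVR12 window empty, Day 168 onward quantifiable | no (filled) | no |
| Negative at Day 84, quantifiable from Day 168 | yes | no |
| Confirmed relapse by Day 84 | no | no |
| Single quantifiable value at Day 84, then negative | no | yes |

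**Step 2: loss after the SVR12 window.** PPV under the SAP = (63 − relapses − losses)/63. Observed-data PPV = (63 − relapses − losses)/(63 − losses). Agreement under the SAP = (63 − relapses − losses + 7)/70.

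| Late relapses | Losses | PPV, SAP | PPV, observed | Agreement, SAP |
|---|---|---|---|---|
| 0 | 0 | 63/63 = 100% | 63/63 = 100% | 70/70 = 100% |
| 0 | 3 | 60/63 = 95.2% | 60/60 = 100% | 67/70 = 95.7% |
| 0 | 6 | 57/63 = 90.5% | 57/57 = 100% | 64/70 = 91.4% |
| 1 | 3 | 59/63 = 93.7% | 59/60 = 98.3% | 66/70 = 94.3% |
| 3 | 0 | 60/63 = 95.2% | 60/63 = 95.2% | 67/70 = 95.7% |
| 3 | 3 | 57/63 = 90.5% | 57/60 = 95.0% | 64/70 = 91.4% |

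Three losses with no relapse and three relapses with no loss give the same PPV and the same agreement. In a 10-subject arm with 9 responders, one loss gives 8/9 = 88.9%.

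**Step 3: filling SVR12 from the SVR24 sample.** Take 3 subjects who are quantifiable from Day 168, and let 0, 1, 2 or 3 of them lack a value in the SVR12 window. PPV is 60/63 = 95.2%, 60/62 = 96.8%, 60/61 = 98.4% and 60/60 = 100%. Agreement rises from 67/70 to 70/70.

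**Step 4: direction of the combined effect.** Assume 6 of the 63 responders are lost later and 4 of the 7 non-responders are unobserved. Agreement under the SAP is (57 + 7)/70 = 91.4%; among observed pairs it is (57 + 3)/60 = 100%. NPV is 7/7 under the SAP and 3/3 among observed pairs, both 100%.

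**Step 5: when missing data dominate.** If a fraction m of SVR12 responders is lost and a fraction r of the rest relapses late, the share of SVR12-yes/SVR24-no cases due to missing data is m/(m + (1 − m)r).

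| m | r = 0 | r = 1% | r = 5% | r = 10% |
|---|---|---|---|---|
| 2% | 100% | 67% | 29% | 17% |
| 5% | 100% | 84% | 51% | 34% |
| 10% | 100% | 92% | 69% | 53% |

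**Step 6: NPV.** A confirmed failure by SVR12 is an SVR24 failure by definition, and a subject with no later data fails by rule. Among the patterns in Step 1, only the single unconfirmed quantifiable value lowers NPV.

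**The case against.** A reader might infer that these statistics measure dropout and the imputation rule and say nothing about prediction. The documents do not support that. Subjects sampled in both windows contribute real concordance, and an observed late relapse lowers PPV. Nor can one say that agreement and NPV are simply inflated: in Step 4 agreement is too low, and NPV is 100% either way.

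The SAP also limits the problem. SVR24 can be filled from PT Week 36 or 48, so only a responder with no later value becomes a missing-data failure. A last negative sample on Days 57–77, after PT Week 8 is due, is enough for SVR12, so leaving before PT Week 12 does not by itself mean failing both. Relapse24 in SAP 10.1 is restricted to SVR12 achievers with SVR24-window data, and relapse after SVR12 is a separate reason for SVR24 non-response. Much of an observed-data PPV can be recovered from these. The recovery is incomplete: Relapse24 uses SVR12 status after filling, excludes re-infection, and gives neither agreement nor NPV. The reasons list is also uncertain on missing data, because its SVR24 premature-discontinuation cut-off of 154 days exceeds the longest regimen (12 × 7 = 84 days).

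SAP 10.6 also states: "All other endpoints will be presented using data as observed". Whether that covers concordance is unclear; the ITT denominator points to imputed status.

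Two further objections stand. Concordance is not an objective, a primary or secondary endpoint, or among the additional endpoints in protocol 8.1.2.3. And replacing the analysis with strict both-window pairs would drop known virologic failures who leave or start new therapy, and could nearly empty the NPV denominator.

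**Conclusion.** The point holds as a modest one. As defined, agreement, PPV and NPV combine virologic concordance with loss to follow-up and imputation, and the reported figure does not show which produced it. With 63 responders and no relapse, an assumed 3 to 6 losses lower PPV from 100% to 95.2–90.5% and agreement to 95.7–91.4%. Loss before the SVR12 window and filling from the SVR24 sample work in the other direction. The net bias cannot be signed or sized from the documents, since they give neither loss nor late-relapse rates. Missing data dominate the discordant cases only if loss exceeds late relapse. NPV near 100% follows largely from the SVR24 definition and is not in itself an error. The primary SVR12 analysis is untouched.

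**What to change.** In SAP 10.6, keep the ITT version and state that it uses imputed SVR status. Add agreement, PPV and NPV on observed data:

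- SVR12 status from an HCV RNA value observed in the SVR12 window, with no flanking or later-value fill.
- SVR24 status from an observed value. State whether a PT Week 36 or 48 value qualifies when the SVR24 window is empty.
- Confirmed virologic failures kept as known failures, even if they have no later sample.
- Missing data not counted as failure.

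Report the number excluded at each step, and add a note that NPV is fixed by definition for confirmed failures.

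The cost is a few sentences, a program filter and one more descriptive table, on a smaller denominator. No new data are needed.

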10.7 Resistance Analyses

If possible, subjects treated with study drug during the Treatment Period who experience virologic failure will have resistance testing conducted if 1) they have on-treatment

breakthrough; 2) if they have post-treatment relapse (irrespective of the time of relapse), with a study drug duration \geq 77 days, 49 days and 38 days for 12-week, 8-week, and 6-week of treatment, respectively; or 3) if they have at least 6 weeks of treatment and fail to suppress by Week 6 (i.e., meet virologic stopping criteria). Subjects meeting one of these criteria will be referred to as subjects in the primary virologic failure (PVF) population, and a listing by subject that includes HCV subtype, IL28B genotype, reason for non-response, time point(s) sequenced as closest to time of VF, and HCV RNA value at the VF time point(s) will be produced for these subjects. In addition, all listings described below will display HCV subtype and reason for non-response in the subject identifier for each subject. A separate listing will delineate all subjects in the PVF population for whom no sequencing was performed (e.g., lost to follow-up while HCV RNA \leq 1000 IU/mL). Subjects treated with study drugs who do not achieve SVR₁₂ who do not meet the above criteria for the PVF population (e.g., those with less than 6 weeks of therapy who failed to suppress), but have a time point with HCV RNA \geq 1000 IU/mL after treatment discontinuation, will have the sample at that time point sequenced.

Only samples with an HCV RNA level of \geq 1000 IU/mL will undergo sequence analysis in order to allow accurate assessment of products of amplification. Therefore if the HCV RNA level at the time of virologic failure (VF) or treatment discontinuation is $<$ 1000 IU/mL, the sample closest in time after the failure/discontinuation with an HCV RNA level \geq 1000 IU/mL will be used if available. Next generation sequencing (NGS) of a given target will be performed only if no variants are detected at signature amino acid positions by population sequencing in that sample. Included time points for analyses on subjects in the PVF and non-PVF population are: 1) time of virologic failure/treatment discontinuation or sample closest in time after failure/discontinuation with an HCV RNA level of \geq 1,000 IU/mL, 2) 24 weeks post-DAA treatment, provided that resistance-associated variants were detected by either population sequencing or NGS at the time of failure/discontinuation, and 3) 48 weeks post-DAA treatment, provided that resistance-associated variants were detected by either population sequencing or NGS at 24 weeks post-DAA treatment. For these samples, NGS will be performed on a given target only if no variants are detected at signature amino acid positions by population sequencing.

The regions of interest for population sequencing and NGS for all samples from subjects who do not achieve SVR₁₂ are those encoding complete NS3/4A, NS5A, and NS5B. The regions encoding NS3 amino acids 1 – 181, NS5A amino acids 1 – 215, and NS5B amino acids 1 – 591 will be sequenced for analysis of baseline samples from the SVR-achieving subjects. An appropriate prototypic reference sequence will be used for comparison with sequences from samples.

The following are considered signature amino acid positions in genotypes 2 and 3: 36, 43, 54, 55, 56, 80, 155, 156, 166 (GT3 only), 168 in NS3; 24, 28, 29, 30, 31, 32, 58, 92, 93 in NS5A; and 142, 159, 237, 282, 289, 320, 321 in NS5B.

The following definitions will be used in the resistance analyses:

- Baseline variant: a variant (by population sequencing) in a baseline sample determined by comparison of the amino acid sequence of the baseline sample to the appropriate prototypic reference amino acid sequence for a given DAA target (NS3, NS5A, or NS5B).
- Post-baseline variant by population sequencing: an amino acid variant in a post baseline time point sample that was not detected at baseline in the subject.
- Variant at signature amino acid position: variant (relative to reference) present in a baseline or a post-baseline sample at a signature amino acid position (for NGS, detectable at 2% detection threshold).
- Emerged variant: a post-baseline variant that is observed in 2 or more subjects of the same subtype by population sequencing or NGS.
- Linked variant by population sequencing: 2 or more signature or emerged amino acid variants identified within a target by population sequencing, and no mixture of amino acids is detected at either position.

Analysis will be performed separately for each HCV subtype and study arms within each listing.

Analysis 1: The following analyses will be performed for all subjects:

- A listing of all baseline variants at signature amino acid positions for each DAA target (NS3, NS5A and NS5B) (ITT population).
- Listing of all baseline variants at non-signature amino acid positions for subjects in PVF population.
- The number and percentage of subjects with each baseline variant at a signature amino acid position within each target out of the total number of baseline samples that were sequenced will be provided (ITT population). This table includes prevalence of each baseline variant, and a summary of number of subjects with variants in NS3 only, in NS5A only, in NS5B only, any in NS3, any in NS5A, any in NS5B, any in NS3 or NS5A or NS5B, any in NS3 + NS5A, any in NS3 + NS5B, any in NS5A + NS5B, any in NS3 + NS5A + NS5B.

Analysis 2: The impact of baseline variants on treatment outcome will be assessed as follows: for each variant, the SVR₁₂ rate will be calculated for subjects with and without the variant and the 2 rates will be compared using Fisher's exact test. Subjects in the non-PVF population will be excluded from this analysis. Analysis will be grouped by (1) study Arm, (2) HCV subtype, (3) DAA target (NS3, NS5A or NS5B).

- Variants at signature amino acid positions (vs no variant at that position).
- Each variant at signature amino acid position (vs not that variant).
- Variants at non-signature amino acid positions (vs no variant at that positions).

Analysis 3: The following analyses will be performed for subjects in the PVF and non-PVF populations who have post-baseline resistance data available.

For analysis by population sequencing, the following tables will be provided:

- Listings by subject of all post baseline variants relative to the baseline amino acid sequence will be provided for each DAA target (NS3, NS5A and NS5B).
- Listings by subject of all emerged variants, by amino acid position and variants within a DAA target in a post-baseline sample relative to the baseline amino acid sequence will be provided for each DAA target.

- Listings by subject of all post-baseline variants at signature amino acid positions relative to the appropriate prototypic reference amino acid sequences will be provided for each DAA target (NS3, NS5A and NS5B).
- A listing by subject and time point of the linked variants by population sequencing for each target will be provided.

For analysis by NGS, the following tables will be provided:

- Listings by subject of all variants at signature amino acid positions in a post-baseline time point for each DAA target (NS3, NS5A and NS5B).

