10.0 Efficacy Analysis

10.1 General Considerations

Analyses will be performed on the intent-to-treat (ITT) population. Sensitivity analyses of the primary endpoint, when applicable, will be performed on the mITT-GT-VF population specified in Section 5.1.1.

Missing data will be imputed as described in Section 6.3 for analyses of the HCV RNA endpoints of SVR.

Plasma HCV RNA levels will be determined for each sample collected by the central laboratory using the Roche COBAS TaqMan® real-time reverse transcriptase-PCR (RT-

PCR) assay v.2.0. For this assay, the lower limit of quantitation (LLOQ) is 25 IU/mL regardless of genotype, and the lower limit of detection (LLOD) varies by genotype. For GT3, the lower limit of detection (LLOD) is 20 IU/mL; for GT2, LLOD is 20 IU/mL. HCV RNA results that are detectable but not quantifiable are reported as "< 25 IU/mL HCV RNA detected" and those that are undetectable are reported as "HCV RNA not detected" in the database.

The notation "HCV RNA < LLOQ" is used to represent all HCV RNA values < 25 IU/mL, including values reported as "HCV RNA not detected" or "< 25 IU/mL HCV RNA detected." HCV RNA \geq LLOQ are all quantifiable values of 25 IU/mL or greater.

IL28B rs12979860 will be resulted as C/C, C/T, or T/T by the central laboratory.

Definitions for Efficacy Endpoints

Note that a confirmed quantifiable post-treatment value is defined as two consecutive post-treatment HCV RNA measurements \geq LLOQ. During treatment, a confirmed quantifiable value is defined as any two consecutive HCV RNA values \geq LLOQ, either both during treatment or at the final treatment measurement and the next consecutive post-treatment measurement.

Breakthrough = confirmed HCV RNA \geq LLOQ after HCV RNA < LLOQ during treatment, or confirmed increase from nadir in HCV RNA (two consecutive HCV RNA measurements $> 1 \log_{10}$ IU/mL above nadir) at any time point during treatment. A single breakthrough value (\geq LLOQ or $> 1 \log_{10}$ IU/mL above nadir) followed by lost to follow-up will be considered a breakthrough (i.e., will not require confirmation).

On-treatment virologic failure = breakthrough or failure to suppress during treatment (all on-treatment values of HCV RNA \geq LLOQ) with at least 6 weeks (defined as study drug duration \geq 36 days) of treatment for 12-week and 8-week treatment or at least 26 days of treatment for 6-week treatment.

RVR (rapid virologic response) = HCV RNA < LLOQ in the Week 4 window.

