10.4 Secondary Efficacy Analyses

The secondary efficacy endpoints are:

- The percentage of subjects in each treatment arm and across all treatment arms with on-treatment virologic failure (breakthrough defined as confirmed HCV RNA \geq LLOQ after HCV RNA < LLOQ during treatment, or confirmed increase from nadir in HCV RNA at any time point during treatment, or failure to suppress during treatment (all on-treatment values of HCV RNA \geq LLOQ) with at least 6 weeks (defined as active study drug duration \geq 36 days) of treatment for 12-week and 8-week treatment or at least 26 days of treatment for 6-week treatment.
- The percentage of subjects with post-treatment relapse (relapse₁₂ defined as confirmed HCV RNA \geq LLOQ between end of treatment and 12 weeks after last actual dose of active study drug (up to and including the SVR₁₂ assessment time point) for a subject with HCV RNA < LLOQ at Final Treatment Visit who completes treatment. Completion of treatment is defined as study drug duration \geq 77 days, 49 days and 38 days for 12-week, 8-week, and 6-week of treatment, respectively.

The numbers and percentages of the subjects with virologic failure during treatment and with post-treatment relapse will be calculated for each arm. The corresponding 2-sided 95% Wilson score confidence intervals for a binomial proportion will be calculated.

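### The resistance section's rule for failure to suppress (SAP 10.7) does not match the SAP's own definition, so an Arm D virologic failure can fall outside the primary virologic failure population

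*SAP*

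**What the plan says.** SAP 10.7 gives three routes into the PVF population: on-treatment breakthrough, relapse after completing treatment (77, 49 or 38 days by regimen), and failure to suppress. The third applies to subjects "if they have at least 6 weeks of treatment and fail to suppress by Week 6 (i.e., meet virologic stopping criteria". It gives no number of days and no separate rule for the 6-week regimen. The same paragraph gives, as its example of SVR12 non-responders outside the PVF population, "those with less than 6 weeks of therapy who failed to suppress". Analysis 2, which compares SVR12 rates with and without each baseline variant, then states: "Subjects in the non-PVF population will be excluded from this analysis".

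SAP 10.1 defines the event differently: "On-treatment virologic failure = breakthrough or failure to suppress during treatment (all on-treatment values of HCV RNA" at or above LLOQ). There is no week deadline. The minimum duration is set by regimen, at "36 days) of treatment for 12-week and 8-week treatment or at least 26 days of treatment for 6-week treatment". SAP 10.4 repeats this for the secondary endpoint, ending "or at least 26 days of treatment for 6-week treatment".

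SAP 10.6 tabulates failure to suppress after at least 6 weeks with another cut-off, the same for all regimens: those with a duration of at least "38 days) will be tabulated along with the subject numbers corresponding to the subjects who failed to suppress".

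**The concern.** One SAP should have one meaning for failure to suppress. Here the efficacy sections adapt it to the 6-week regimen and the resistance section does not. The relapse route in the same sentence of 10.7 is regimen-specific, and SAP 12.2 records that exposure intervals and the end-of-treatment response were updated for arms of different length. Neither 12.1 nor 12.2 gives a reason for a separate Week 6 rule, so this looks like an incomplete update rather than a choice.

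The stake is a report that contradicts itself. An Arm D subject could be counted as an on-treatment virologic failure in the secondary endpoint and in the reasons for SVR12 non-response, and yet be absent from the population that 10.7 uses for primary virologic failures. A baseline variant carried by that subject would then drop out of the one analysis meant to relate baseline variants to outcome.

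**Working it through.** The SAP gives no figure to reproduce. The check sets the definitions and visit windows side by side.

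**Step 1: is there a Week 6 visit?** (SAP Tables 2, 3 and 4)

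| Regimen | Arms | Visits | Window containing Day 42 |
|---|---|---|---|
| 12 weeks | A, B, E, F | 1, 2, 4, 8, 10, 12 | Week 4 (days 22–42) |
| 8 weeks | C | 1, 2, 4, 8 | Week 4 (days 22–42) |
| 6 weeks | D | 1, 2, 4, 6 | Week 6 (days 36–49) |

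Outside Arm D, failure by Week 6 rests on the Week 4 value or on an unscheduled sample. The next scheduled window starts at day 43.

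**Step 2: which durations count in 10.1 but not in 10.7?** Let t be the day count meant by at least 6 weeks in 10.7. It is not stated there. The candidates are 36 (10.1 and 10.4), 38 (10.6) and 42 (literal, 6 × 7). The gap runs from the 10.1 minimum to t − 1.

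| Reading of t | Arm D (10.1 minimum 26) | 12- and 8-week arms (10.1 minimum 36) |
|---|---|---|
| 36 | days 26–35 (10 values) | none |
| 38 | days 26–37 (12 values) | days 36–37 |
| 42 | days 26–41 (16 values) | days 36–41 |

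Arm D has a gap under every reading. The other arms have one only if t is 38 or 42.

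**Step 3: follow an Arm D subject in the gap who does not reach SVR12.**
- SAP 10.4: on-treatment virologic failure.
- SAP 10.1, reasons for SVR12 non-response: category 1, on-treatment virologic failure.
- SAP 5.1.1 and 10.5: kept in mITT-GT-VF, which removes only non-responders for other reasons.
- SAP 10.7: non-PVF, so absent from the PVF listing, from the Analysis 1 listing of non-signature baseline variants (PVF only), and from Analysis 2.
- SAP 10.7: still sequenced if HCV RNA is at least 1000 IU/mL after discontinuation, still in the Analysis 1 signature-position outputs (ITT), and in Analysis 3 if post-baseline resistance data exist.

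**Step 4: size.** Arm D has about 10 subjects (SAP 4.2). Taking the 90% in SAP 4.3 as an assumption (it is an illustrative observed rate for the Wilson interval), failures of all kinds number 10 × (1 − 0.90) = 1. If that one failure falls in the gap, 10.4 reports 1/10 on-treatment failure while Analysis 2 runs on 9/9 responders, and with no failures every Fisher p is 1. If the subject is kept and is the only carrier of a variant, p = 1/10 = 0.10, the smallest value attainable with one failure in 10. The correction changes what is displayed; it cannot produce p < 0.05 in that setting.

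**The case against.** The strongest reply is that this is a small wording mismatch in an exploratory analysis. Only non-suppressors who stop between 26 days and 6 weeks are affected, in one arm of about 10 that opens only if no more than one Arm C completer relapses through post-treatment Week 4. Breakthrough, relapse after completion and full-course non-suppression all still enter the PVF population. This stands, and it limits the size of the point. It does not remove the contradiction, because 10.7 names the shorter non-suppressors as non-PVF.

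A reader might infer more in four places. The documents do not support these readings.
- *The criterion cannot be applied in the 12- and 8-week arms.* Week 6 is a deadline, not a named visit. A subject there with at least 6 weeks of drug and every value at or above LLOQ has failed to suppress by then. What remains is ambiguity about which sample decides, and about the day count.
- *Slow responders, quantifiable at Week 4 and suppressed at Week 8, would be listed as failures.* The opening sentence of 10.7 limits all three routes to subjects with virologic failure, and the listing needs a reason for non-response. The criterion read alone is loose, but this outcome is not established.
- *The SAP contradicts the protocol's stopping rule across the study.* Protocol 5.4.1.1 uses Week 8 where 10.7 equates Week 6 with the stopping criteria. The supplied protocol covers only Arms A and B at 12 weeks, and the SAP refers to a latest protocol version that is not supplied. The mismatch is shown for those two arms only.
- *Affected subjects are lost from the resistance work.* They are not; step 3 shows where they remain.

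**Conclusion.** The point holds as an internal inconsistency. Criterion 3 of the PVF definition conflicts with the on-treatment virologic failure definition in 10.1 and 10.4. In Arm D it reclassifies non-suppressors with 26 days to less than 6 weeks of drug, on any reading of 6 weeks. Wherever such a subject occurs, the text as written takes a failure that the SAP itself recognises out of Analysis 2 and the PVF listings. The number affected is likely to be none or one, and the consequence is descriptive. The primary SVR12 analysis is untouched.

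The conclusion rests on the text of 10.7 being followed literally, including its non-PVF example. The count rests on about 10 subjects in Arm D and an assumed SVR12 rate near 90%, which the SAP uses only for illustration. The Week 6 and Week 8 passages on stopping criteria must be reconciled; no view is taken here on which is right.

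**What to change.** - In 10.7, define criterion 3 as meeting the failure-to-suppress part of on-treatment virologic failure in 10.1: all on-treatment HCV RNA at or above LLOQ, with study drug duration of at least 36 days for the 12- and 8-week regimens or at least 26 days for the 6-week regimen.
- Change the non-PVF example in the same paragraph to match.
- Remove the Week 6 deadline and the parenthesis about stopping criteria from this analysis definition. Reconcile the stopping criteria with the current protocol separately.
- Bring the 38-day failure-to-suppress cut-off in 10.6 into line with 10.1 in the same edit; otherwise the SAP keeps two meanings of 6 weeks.

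With these changes the gap in step 2 is zero days in every arm. The cost is a few sentences in the SAP and the matching programming specification. No new data are needed.
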